7 EFFICACY VARIABLES AND ANALYSES

7.1 Overview

The primary efficacy variable of the study is the absolute change of the mSLEDAI-2K score from baseline to Month 6. Changes for all time points from Month 1 through Month 6 will be derived and included in the statistical analysis model of the primary endpoint.

There are two secondary endpoints that are analyzed in hierarchical manner for each dose level comparison following any rejections of dose level comparisons hypotheses of the primary endpoint:

- Response at Month 6 on SRI-4 defined as follows:
 - Reduction from baseline of at least 4 points in the mSLEDAI-2Kand
 - No new BILAG A organ domain score and no more than one new BILAG B organ domain score compared with baselineand
 - No increase of more than 0.3 points on the PGA since baseline.
- Response (no worsening) at Month 6 on BILAG-2004 disease activity index defined as no new BILAG A organ domain score and no more than one new BILAG B organ domain score compared with baseline.

The other efficacy endpoints are described as follows:

- Response at Month 6 on the mSLEDAI-2K score defined as a reduction from baseline of at least 4 points.
- Response (no worsening and improvement) at Month 6 on BILAG-2004 disease activity index defined as follows:

- No new BILAG A organ domain score and no more than one new BILAG B organ domain score compared with baseline
- and
- Any BILAG A organ domain score at study baseline improved to B/C/D or any BILAG B organ domain score at study baseline improved to C/D.
- Response at Month 6 on SRI-5, -6, -7, -8 defined as the secondary endpoint (response at Month 6 on SRI-4) with reductions in mSLEDAI-2K of 5, 6, 7 and 8, instead of a reduction of 4.
 - Occurrence of mild, moderate and severe flares from baseline up to Month 6.
 - Time to first severe flare from baseline to Month 6 (severe flares defined as BILAG A organ domain score presence due to items that are new or worse).
 - Time to first flare from baseline to Month 6.
 - Change from baseline to Month 6 in PGA score.

Exploratory endpoints will be analyzed from baseline to a maximum of 12 months on all available assessments according to two groups:

- Group 1: All randomized subjects, for whom baseline is defined as the last available measurement before the start of randomized treatment in TP1.
- Group 2: Subjects re-randomized at Month 6, for whom baseline is defined as the last available measurement before the start of re-randomized treatment in TP2.

Endpoints for Group 1:

- Sustained mSLEDAI-2K response defined as a reduction of at least [REDACTED]
[REDACTED]
[REDACTED]
[REDACTED]
- Change from baseline to each post-baseline assessment up to Month 12 in prednisone or equivalent dose.

Endpoints for Groups 1 and 2:

- Change from baseline to each post-baseline assessment up to Month 12 in mSLEDAI-2K score.
- Response at each post-baseline assessment on improvement in the mSLEDAI-2K score, defined as a reduction from baseline of at least 4 points.
- Response (no worsening and improvement) at each post-baseline assessment on BILAG-2004 disease activity index defined as follows:
 - No new BILAG A organ domain score and no more than one new BILAG B organ domain score compared with baseline

and

- Any BILAG A organ domain score at study baseline improved to B/C/D or any BILAG B organ domain score at study baseline improved to C/D.
- Response at each post-baseline assessment on SRI-4, -5, -6, -7, -8.
- Change from baseline to each post-baseline assessment in PGA score.
- Occurrence of flares and severe flares at each post-baseline assessment (defined as either 1 or more new BILAG A or 2 or more new BILAG B organ domain scores compared to the previous visit).
- Time to first severe flare from baseline to Month 12 (severe flares defined as BILAG A organ domain score presence due to items that are new or worse).
- Time to first flare from baseline to Month 12.

The PRO/QoL endpoints are defined as follows:

- Change from baseline to each post-baseline assessment in FACIT-Fatigue Scale score.
- Change from baseline to each post-baseline assessment in PGIS-F.
- PGIC-F score at each post-baseline assessment.
- Change from baseline to each post-baseline assessment in SF-36v2™.
- Change from baseline to each post-baseline assessment in the Lupus QoL questionnaire.

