5.2 Baseline

- The **‘Baseline (TP1)’** value for **efficacy and safety analyses** is defined as the last non-missing value recorded prior to first study drug intake in TP1 for each endpoint and each subject individually. For subjects that were randomized but did not take any study drug, baseline (TP1) is defined as the last non-missing value recorded up to and including the day of Randomization.
- The **‘Baseline (TP2)’** value for **efficacy and safety analyses** is defined as the last non-missing value recorded up to and including the day of re-randomization for each endpoint and each subject individually. This baseline is only defined for subjects that have been re-randomized by IXRS.

For certain datasets/analyses an **‘intra-day baseline’** is derived (e.g., ECG, vital signs). This intra-day baseline is defined as the last non-missing assessment prior to study drug intake on the corresponding day. If there is no pre-dose assessment on the day (by time and date), then the intra-day baseline is considered to be missing. The intra-day baseline is calculated for parameters that are part of the hourly measurements on the day of first study drug intake (in TP1) and the day of first study drug intake of a re-initiated subject (in TP1).

For datasets where multiple measurements exist for the selection of the baseline assessment, the definition(s) is/are provided in the corresponding sections (e.g., spirometry or ECG data).

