7.5.4.1 Variables

Group 1

The variable is derived as defined in Section 7.4.2 for each visit up to Month 12.

Group 2

The variable is derived as defined in Section 7.4.2 for each visit from Month 6 up to Month 12 based on the TP2 baseline value for all subjects in FAS-TP2.

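### Group 2 BILAG-2004 response: SAP 7.1 measures improvement from study baseline and SAP 7.5.4.1 from the TP2 baseline, so a re-randomized subject can be a responder under one rule only

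*SAP*

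**What the plan says.** SAP Section 7.1 lists this response under the label "Endpoints for Groups 1 and 2", with one definition for both. The no-worsening part reads "No new BILAG A organ domain score and no more than one new BILAG B organ domain score compared with baseline". The improvement part reads "Any BILAG A organ domain score at study baseline improved to B/C/D", or "any BILAG B organ domain score at study baseline improved to C/D". So the first part refers to baseline and the second to *study baseline*. Section 5.2 defines a TP1 baseline and a TP2 baseline, but no study baseline.

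Section 7.5.4.1 says that the Group 2 variable follows Section 7.4.2 "for each visit from Month 6 up to Month 12 based on the TP2 baseline value for all subjects in FAS-TP2". Section 7.4.2.1 adds that a subject with no A or B domain at baseline is a responder on the improvement part. Section 7.5.4.2 then compares the two ex-4 mg arms over Months 7 to 12.

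The TP2 baseline itself has two cut-offs. Section 7.1 describes Group 2 as subjects "for whom baseline is defined as the last available measurement before the start of re-randomized treatment in TP2", and Sections 2.4.2 and 7.5 agree. Section 5.2 uses the "last non-missing value recorded up to and including the day of re-randomization".

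**The concern.** Two programmers could each follow the SAP and produce different responder flags for the same subject. The choice also bears on meaning. Section 3.3 says that the re-randomized part is there to explore dose reduction and withdrawal after 4 mg. A subject who improved from B to C on 4 mg enters TP2 with no A or B. If 7.5.4.1 is combined with the default in 7.4.2.1, that subject is already an improvement responder. One new B is tolerated by the no-worsening part, so the subject stays a responder after relapsing to the grade held at study entry. Under 7.1 the same subject is a non-responder.

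**Working it through.** The SAP states no expected rate for this endpoint, so there is no plan figure to reproduce. The check compares the two definitions.

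**Rules.** Let S, T and V be the grade at study (TP1) baseline, at TP2 baseline and at a TP2 visit. Both rules judge no worsening from T to V. Rule 7.1 judges improvement from S to V; rule 7.5.4.1 judges it from T to V. Assumed here: a new A is A at V but not at T; a new B is B at V with C, D or E at T.

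**Single-domain examples (no A or B in any other domain).**

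| S–T–V | No worsening | Improvement, 7.1 | Improvement, 7.5.4.1 | Responder under |
|---|---|---|---|---|
| A–B–B | met | A to B: yes | B to B: no | 7.1 only |
| B–A–B | met | B to B: no | A to B: yes | 7.5.4.1 only |
| B–C–B | met (one new B allowed) | B to B: no | no A/B at T: yes by default | 7.5.4.1 only |

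The first two rows do not depend on the default. The third does: if subjects with no A or B at TP2 baseline were scored non-responders, B–C–B would be a non-responder under both rules.

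**All single-domain paths.** Five grades at three times give 5 × 5 × 5 = 125 paths. With the 7.4.2.1 default, 13 respond only under 7.1 and 10 only under 7.5.4.1, so 23 are discordant. Without it the counts are 16 and 16, so 32. These are possible paths, not expected proportions of subjects.

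**Illustration of size. Every rate is assumed; none comes from the documents.** Take one B domain at study baseline, with relapse only to B. Let 55% be improved to C or D at Month 6. Let relapse in TP2 be 40% on placebo and 15% on 2 mg, and new improvement among the rest 10% and 20%.

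- Rule 7.1: improved × (1 − relapse) + not improved × new.
  - Placebo: 0.55 × 0.60 + 0.45 × 0.10 = 0.375.
  - 2 mg: 0.55 × 0.85 + 0.45 × 0.20 = 0.558.
  - Difference: about 18 points.
- Rule 7.5.4.1 with the default: improved + not improved × new.
  - Placebo: 0.55 + 0.45 × 0.10 = 0.595.
  - 2 mg: 0.55 + 0.45 × 0.20 = 0.640.
  - Difference: 4.5 points.
- Rule 7.5.4.1 with the default reversed to non-responder: 0.45 × 0.10 = 0.045 and 0.45 × 0.20 = 0.090, again 4.5 points.

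**Subjects concerned.** 325 / 5 = 65 randomized to 4 mg, and 65 / 2 = 32.5. That is at most about 32 per ex-4 mg arm, since only subjects still on 4 mg at Month 6 are re-randomized.

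**Cut-off.** Cross the grade at each of the two cut-offs with the visit grade: 20 of 125 combinations change responder status, and all 20 need different grades at the two cut-offs. If both cut-offs select the same assessment, nothing changes. SAP Appendix 12.1 schedules no BILAG between Month 6 and Month 7 except at unscheduled visits.

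**The case against.** The strongest reply is that the operative rule is clear. Section 7.1 is an overview and sets the Group 2 baseline at TP2 shortly before the list. Section 7.5.4.1 is explicit, and the other Group 2 change and response endpoints also use the TP2 baseline. The phrase *study baseline* repeats the Month 6 bullet, where it can only mean TP1, and may simply have been carried over. This stands as a reason why the sponsor may prefer the TP2 baseline throughout. It does not remove the conflict in the current text. Rewording 7.1 alone would also leave the default rule in force, so that B–C–B still counts as response.

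A reader might infer that the endpoint cannot show loss of the 4 mg benefit. The documents do not support that. A new A, or two new Bs, against the TP2 baseline is still non-response. Group 1 derives the same endpoint from TP1 baseline up to Month 12, and Section 5.4.3.3, to which its analysis points, lists both ex-4 mg arms (although Section 7.5.4.2 speaks of five groups and that list has six). Group 2 mSLEDAI-2K, SRI, PGA and flare endpoints also address withdrawal.

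A reader might also infer that the two cut-offs matter in practice. A remote Month 6 visit with home delivery of drug could in principle place an assessment between them, but no text describes re-randomization at a remote visit, and the COVID-19 addendum is limited in scope and duration.

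**Conclusion.** The concern holds as an inconsistency in one exploratory endpoint. The two sections give different responder status on identifiable grade paths. A–B–B and B–A–B are discordant whatever is done about the default; B–C–B is discordant because of the default in 7.4.2.1. The consequence that matters is that a relapse to one B domain after withdrawal of 4 mg can be reported as a response.

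The percentages show only that the gap between arms can shrink. They rest on assumed rates and on a one-domain setting in which the no-worsening part cannot fail, so they do not predict the trial's result. The cut-off mismatch is minor and should rarely change a value. The primary and secondary endpoints and their Type I error control are unaffected.

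**What to change.** State the same Group 2 reference for each part of the response in both 7.1 and 7.5.4.1, and replace *study baseline* with a term defined in 5.2. Either of these would do:

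- (a) Judge no worsening against the TP2 baseline and improvement against the TP1 baseline, as 7.1 reads. B–C–B is then a non-responder.
- (b) Use the TP2 baseline throughout, reword 7.1, and do not apply the 7.4.2.1 default to Group 2. For example, restrict the improvement part to subjects with an A or B at TP2 baseline. This matches the other Group 2 endpoints, but the improvement part then says nothing about subjects who entered TP2 free of A and B. Under the assumed 55% it would rest on about 0.45 × 32.5 = 15 subjects per arm.

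Either choice gives each grade path a single classification.

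As a minor change, align 5.2 with 2.4.2, 7.1 and 7.5: define the TP2 baseline as the last non-missing value before the first TP2 dose, and keep the day of re-randomization as the fallback for re-randomized subjects never dosed in TP2. Section 5.2 already has this structure for TP1. The change also reaches the TP2 safety baselines (laboratory, spirometry, ECG, blood pressure, weight), so it should be recorded there.

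The cost is a few lines of SAP text and a small derivation change, with no new data.

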7.1.1 Overall testing strategy

The Type I error rate will be controlled for the testing of multiple null hypotheses associated with the primary and secondary endpoints and the four dose levels included in this study: 0.5, 1, 2, and 4 mg.

The four statistical null hypotheses associated with the primary efficacy endpoint are:

Change of mSLEDAI-2K from baseline to Month 6:

- $H1_{\text{mSLEDAI-2K}}$: cenerimod_{0.5 mg} – placebo = 0
- $H2_{\text{mSLEDAI-2K}}$: cenerimod_{1.0 mg} – placebo = 0
- $H3_{\text{mSLEDAI-2K}}$: cenerimod_{2.0 mg} – placebo = 0
- $H4_{\text{mSLEDAI-2K}}$: cenerimod_{4.0 mg} – placebo = 0

The four alternative hypotheses are:

- $HA1_{\text{mSLEDAI-2K}}$: cenerimod_{0.5 mg} – placebo \neq 0
- $HA2_{\text{mSLEDAI-2K}}$: cenerimod_{1.0 mg} – placebo \neq 0
- $HA3_{\text{mSLEDAI-2K}}$: cenerimod_{2.0 mg} – placebo \neq 0

- $HA4_{mSLEDAI-2K}: cenerimod_{4.0\text{ mg}} - placebo \neq 0$

These hypotheses represent the difference in mean change from baseline to Month 6 in mSLEDAI-2K between the four doses of cenerimod and placebo.

The eight statistical null hypotheses / alternative hypotheses associated with the secondary efficacy endpoints are:

SRI-4

- $H1_{SRI-4}: cenerimod_{0.5\text{ mg}}/placebo = 1$
- $H2_{SRI-4}: cenerimod_{1.0\text{ mg}}/placebo = 1$
- $H3_{SRI-4}: cenerimod_{2.0\text{ mg}}/placebo = 1$
- $H4_{SRI-4}: cenerimod_{4.0\text{ mg}}/placebo = 1$

vs

- $HA1_{SRI-4}: cenerimod_{0.5\text{ mg}}/placebo \neq 1$
- $HA2_{SRI-4}: cenerimod_{1.0\text{ mg}}/placebo \neq 1$
- $HA3_{SRI-4}: cenerimod_{2.0\text{ mg}}/placebo \neq 1$
- $HA4_{SRI-4}: cenerimod_{4.0\text{ mg}}/placebo \neq 1$

and

BILAG-2004

- $H1_{BILAG}: cenerimod_{0.5\text{ mg}}/placebo = 1$
- $H2_{BILAG}: cenerimod_{1.0\text{ mg}}/placebo = 1$
- $H3_{BILAG}: cenerimod_{2.0\text{ mg}}/placebo = 1$
- $H4_{BILAG}: cenerimod_{4.0\text{ mg}}/placebo = 1$

vs

- $HA1_{BILAG}: cenerimod_{0.5\text{ mg}}/placebo \neq 1$
- $HA2_{BILAG}: cenerimod_{1.0\text{ mg}}/placebo \neq 1$
- $HA3_{BILAG}: cenerimod_{2.0\text{ mg}}/placebo \neq 1$
- $HA4_{BILAG}: cenerimod_{4.0\text{ mg}}/placebo \neq 1$

These eight hypotheses represent the ORs of the secondary endpoints SRI-4 and BILAG-2004 between the four doses of cenerimod and placebo.

Each null hypothesis will be tested against the alternative hypothesis that the OR is different from 1 between cenerimod and placebo, at a given dose, in SRI-4 and BILAG-2004.

[figure not shown]
Within each primary and secondary endpoint analysis, the Hochberg procedure will be used to control the familywise error rate to ensure an overall two-sided Type I error rate of 5% for the four treatment group comparisons vs placebo. Further control of the study-wise error rate is conducted such that, for a given hypothesis to be rejected at a two-sided Type I error rate of 5%, the same dose-level hypothesis must have also been rejected for the previous endpoint(s), considering the above ordering of the endpoint hypotheses [see Figure 2].

This testing strategy protects the Type I error rate in the primary endpoint family with a slight increase in the Type I error rate in the secondary endpoint families.

Testing all four null hypotheses in the secondary endpoint families irrespective of which dose groups were significant in the previous endpoint family is the conservative approach (as opposed to only testing the significant doses from the previous endpoint family).

Claims for statistical significance will not be made on results from dose groups that have not been significant in a previous endpoint family. Such results are considered exploratory only.

Figure 2 Control of Type I error rate within each endpoint and treatment group

(a) The Hochberg procedure is used to control the familywise error rate for the four dose comparisons vs. placebo within each endpoint (grouped in rectangles).

(b) Further control of Type I error rate is ensured in a hierarchical manner for each dose comparison. To obtain statistical significance the p-value must be less than 0.05 for the hypothesis of interest and all previous hypotheses in the hierarchy (descending arrows).

1

BILAG 2004 = British Isles Lupus Assessment Group-2004; mSLEDAI-2K = modified Systemic Lupus Erythematosus Disease Activity Index-2000; SRI = Systemic Lupus Erythematosus Responder Index.

7.2 Primary endpoint analysis

7.2.1 Overview of analyses

The main estimator as well as sensitivity and supplementary estimators for the primary estimand as defined in Section 3.1.1 are summarized in Table 5.

Table 5 Overview of analyses for primary estimand

Estimator	Section	Endpoint	Imputation method	Analysis
Main estimator	7.2.5	Change of mSLEDAI-2K from baseline to Month 6	None (MAR assumption)	Primary analysis (MMRM model) using the FAS. To ensure that the estimand based on the treatment policy strategy can be estimated, the value for the variable of change in mSLEDAI-2K is used regardless of occurrence of intercurrent events, such as treatment discontinuation.
Sensitivity estimator #1	7.2.6.1	Change of mSLEDAI-2K from baseline to Month 6	Multiple imputation under MAR	Simulation of 100 datasets based on MMRM model
Sensitivity estimator #2	7.2.6.2	Change of mSLEDAI-2K from baseline to Month 6	Multiple imputation under MNAR using copy reference	Simulation of 100 datasets based on MMRM model
Sensitivity estimator #3	7.2.6.3	Change of mSLEDAI-2K from baseline to Month 6	Multiple imputation under MNAR using jump to reference	Simulation of 100 datasets based on MMRM model
Sensitivity estimator #4	7.2.6.4	Change of mSLEDAI-2K from baseline to Month 6	None (MAR assumption)	Primary analysis (MMRM model) based on PPS
Sensitivity estimator #5	7.2.6.6	Change of mSLEDAI-2K from baseline to Month 6	None (MAR assumption)	Primary analysis (MMRM model) based on complete case analysis
Supplementary estimator #1 (dose response)	7.2.6.9	Dose response of mSLEDAI-2K from baseline to Month 6	None (MAR assumption)	
Supplementary estimator #2 (hypothetical estimand)	7.2.6.7	Change of mSLEDAI-2K from baseline to Month 6 (hypothetical estimand)	None (MAR assumption)	Primary analysis (MMRM model) for all on-treatment data. To ensure that the estimand based on the hypothetical strategy can be estimated, only values of mSLEDAI-2K prior to

Estimator	Section	Endpoint	Imputation method	Analysis
				occurrence of treatment discontinuation, the intercurrent event of interest, are used.
Supplementary estimator #3 (SLEDAI-2K)	7.2.6.8	Change of SLEDAI-2K from baseline to Months 1, 2, 3, 4, 5 and 6	None (MAR assumption)	Primary analysis (MMRM model)
Supplementary estimator #4 (subgroups)	7.2.7	Change of mSLEDAI-2K from baseline to Month 6	None (MAR assumption)	Subgroup analyses
Supplementary estimator #5 (response over time)	7.2.6.5	Change of mSLEDAI-2K from baseline to Months 1, 2, 3, 4, 5 and 6	None (MAR assumption)	Primary analysis (MMRM model)

FAS = Full Analysis Set; MAR = missing at random; MMRM = mixed model for repeated measures; MNAR= missing not at random; mSLEDAI-2K = modified Systemic Lupus Erythematosus Disease Activity Index-2000; PPS = Per-Protocol Set.

7.2.2 Variables

The primary efficacy endpoint is the absolute change from baseline to Month 6 in the mSLEDAI-2K score.

The null hypotheses for the primary endpoint will be tested using an MMRM on the change from baseline in mSLEDAI-2K for all available post-baseline scores from Months 1 to 6. This change is defined as the difference:

$$\text{Change in mSLEDAI-2K} = \text{post-baseline mSLEDAI-2K score} - \text{baseline mSLEDAI-2K score.}$$

Post-baseline visits will be assigned into time windows, as defined in Section 5.4.4, and the change from baseline will be computed based on the assigned visit labels.

Following the treatment policy estimand all data will be included in the analysis regardless of early treatment discontinuation or other intercurrent events.

The mSLEDAI-2K score is derived on the mSLEDAI-2K eCRF page for every visit and can be used without further derivation.

7.2.3 Handling of missing data

Based on the Phase 2 study, AC-064A201, it is expected that 6% of subjects will have a missing mSLEDAI-2K result at Month 6.

Missing data will not be imputed but will be handled by the MMRM assuming that the data are MAR.

Various sensitivity analyses will be performed to evaluate the robustness of this assumption [see [Table 5](#)].

A summary of the patterns of missingness from baseline up to Month 6 will be provided as well as a figure presenting the mean change from baseline in mSLEDAI-2K for study completers and withdrawals by reason.

7.2.4 Hypothesis, statistical model and assumptions

The hypotheses for the primary endpoint mSLEDAI-2K are presented in Section [7.1.1](#).

7.2.5 Main analysis

The primary statistical analysis will be performed using the FAS, according to the intention-to-treat approach.

The null hypotheses for the primary endpoint will be tested using an MMRM on all available changes from baseline in mSLEDAI-2K for post-baseline scores from Months 1 through 6.

The following fixed effects will be included in the model:

- Treatment group.
- Month.
- Baseline mSLEDAI-2K score.
- Treatment group by month interaction.
- Baseline mSLEDAI-2K score by month interaction (as continuous variable).
- Stratification factor OCS (from IXRS).

The stratification factor mSLEDAI-2K at Screening will not be included in the model as the continuous baseline value is already included in the model.

A restricted maximum likelihood approach in combination with the Newton Raphson Algorithm will be used.

An unstructured (UN) covariance matrix will be used to account for the correlation between repeated measurements from the same subject. If this analysis fails to converge, the following structures will be tested in a subsequent order until model-convergence is achieved: heterogeneous Toeplitz (TOEPH); Toeplitz (TOEP); autoregressive (AR(1)); compound symmetry (CS). The Kenward-Roger approximation will be used to estimate denominator degrees of freedom.

The treatment effect for each cenerimod dose vs placebo will be estimated from the LSM differences for each dose vs placebo at Month 6 and their corresponding 95% CIs.

The hypothesis tests will be based on the associated p-values at the two-sided significance level of alpha of 5%, controlling for multiplicity using the Hochberg procedure as mentioned above.

This analysis will be implemented using the following SAS[®] code:

```
proc mixed method=reml;
  class subjid ocs treatment month;
  model change = ocs sledai_bl treatment month treatment*month sledai_bl*month / ddfm=kr;
  repeated month / type = UN subject=subjid(treatment);

  slice treatment*month / sliceby=month pdiff cl;
run;
```

Efficacy data of the primary endpoint will be summarized descriptively and listed using the FAS.

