2 STUDY DESIGN AND FLOW

2.1 Study design

This is a Phase 2b, multicenter, randomized, double-blind, placebo-controlled, parallel group study to evaluate the efficacy, safety, and tolerability of cenerimod in subjects with moderate to severe SLE.

Approximately 325 adult subjects with SLE will be randomized in a 1:1:1:1:1 ratio to placebo, 0.5, 1, 2, or 4 mg once daily of cenerimod, in addition to background SLE therapy.

Once randomized, all subjects will enter a 6-month double-blind study treatment period defined as Treatment Period 1 (TP1).

Subjects randomized to, and still receiving, placebo, 0.5, 1, or 2 mg at Month 6 will continue their study treatment up to an additional maximum of 6 months in Treatment Period 2 (TP2), for a total maximum of 12 months.

Subjects randomized to the 4 mg arm will receive study treatment at this dose for a maximum of 6 months in TP1. Afterwards, subjects in this group, still receiving this dose

at Month 6, will be re-randomized in a 1:1 ratio to placebo or cenerimod 2 mg to enter TP2 and will continue for a total maximum of 12 months

Subjects who discontinue treatment in TP1 will continue study FU, performing study assessments, up to maximum duration of 12 months.

At EOT, subjects will enter a 6-month FU period (4-month before protocol Version 5).

Treatment allocation is stratified by dose of OCS at Randomization (two strata: < 7.5 mg/day or ≥ 7.5 mg/day prednisone or equivalent), and by disease activity at Screening (with two strata: mSLEDAI-2K < 10 or ≥ 10).

The study will be conducted at approximately 180 sites in 21 countries notably from the regions of Asia Pacific, Eastern Europe, Latin America, North America, and Western Europe.

No interim analysis is planned. There will be three study analyses: the Month-6 analysis, the Month-12 analysis and the final EOS analysis. Month-6 analysis will be performed when all randomized subjects have completed TP1 or discontinued the study. Month-12 analysis will be performed when all randomized subjects have completed TP2 or discontinued the study. Final EOS analysis will be performed when all randomized subjects have completed the post-treatment follow-up period or discontinued the study.

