2.3 Study periods

2.3.1 Screening period

The screening period starts with the signing of the informed consent form and ends on the day of Randomization, before the first study drug intake. This period can last up to 60 days.

During this period, the subject's SLE background medication should be maintained stable except for OCS which should be tapered to the minimum required dose and maintained stable for at least 15 days prior to Randomization [see protocol section 5.2.2.1, [D-22.031](#)].

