6.8.2 Stratification variables

6.8.2.1 Variables

OCS are collected on the Previous/Concomitant Medications eCRF page and are identified via coding. The stratification variable ‘Dose of oral corticosteroids’ is derived as a binary variable (< 7.5 mg/day vs ≥ 7.5 mg/day) at Randomization.

The mSLEDAI-2K data is collected on the mSLEDAI-2K eCRF page at Screening. mSLEDAI-2K is also derived as a binary variable (< 10 and ≥ 10).

The stratification variables, as entered by the investigator, are transferred by the IXRS provider.

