7.4.7.2 Analysis

An MMRM model will be used to analyze this endpoint including all monthly visits (similar to primary efficacy analysis in Section 7.2.5).

The following fixed effects will be included in the model: PGA baseline value, the two stratification factors (OCS and mSLEDAI-2K from IXRS), treatment group, month, treatment group by month interaction and PGA baseline value by month interaction.

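### The primary MMRM leaves out the mSLEDAI-2K randomization stratum because baseline is in the model, but the stratum comes from Screening and baseline is normally a later reading; adding it is a small, nearly free gain

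*SAP*

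**What the plan says.** - **Stratum.** SAP 2.1 stratifies allocation by OCS dose at Randomization and "by disease activity at Screening (with two strata: mSLEDAI-2K < 10 or ≥ 10"). SAP 6.8.2.1 gives the source: "The mSLEDAI-2K data is collected on the mSLEDAI-2K eCRF page at Screening". The stratum value itself is what the investigator entered in IXRS.
- **Covariate.** SAP 5.2 takes Baseline (TP1) as the "last non-missing value recorded prior to first study drug intake in TP1".
- **Timing.** Appendix 12.1 marks mSLEDAI-2K at both Visit 1 (Screening) and Visit 2 (Randomization). SAP 2.3.1 allows up to 60 days of screening, during which OCS should be "tapered to the minimum required dose and maintained stable for at least 15 days prior to Randomization".
- **Primary model.** SAP 7.2.5 lists treatment, month, continuous baseline, their interactions with month, and the OCS stratum. On the other factor it says: "The stratification factor mSLEDAI-2K at Screening will not be included in the model as the continuous baseline value is already included in the model". The SAS code agrees.
- **Elsewhere.** No sensitivity or supplementary analysis of the whole sample in Table 5 adds the stratum. It does serve as a subgroup variable for the primary endpoint (5.5, 7.2.7).

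**The concern.** A stratum can be left out as redundant when a covariate in the model determines it. Here the two come from different visits. SAP 6.8.3.3.1 describes the index as covering the preceding 10 days, so readings several weeks apart can describe different episodes of disease activity. A subject can be allocated in the upper stratum and have a baseline below 10, or the reverse.

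Two things are at stake, both modest. If the Screening category predicts Month 6 beyond baseline, that variance stays in the error term of all four dose comparisons. And the balance that stratification imposed is not fully credited, so the reported standard errors would be slightly too large.

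**Working it through.** **No plan figure to reproduce.** The supplied documents give no SD, no power and no correlations. The SAP points to protocol section 10.5 for the target difference, and that section is not among them. What follows is an illustration on assumptions.

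**Does baseline determine the stratum?** No, from the sections set side by side above. They coincide only if the Randomization score is missing, in which case baseline falls back to Screening, or if no subject crosses 10 between visits. For scale only: for a bivariate normal pair cut at the median, the share on different sides is arccos(r)/π, which is 14% at r = 0.9 and 30% at r = 0.6. The percentile at which 10 falls in this trial is not given.

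**Residual variance removed.** With baseline as a covariate, modelling change or the Month 6 score gives the same residuals. Treat Screening S, baseline B and Month 6 score Y as standard normal, with the cut at c, p = P(S ≥ c) and φ the normal density at c. The share of the residual variance of Y given B that the stratum removes is

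φ²(r_SY − r_SB·r_BY)² / {[p(1 − p) − r_SB²φ²](1 − r_BY²)}.

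- *Floor.* If Screening predicts Month 6 only through baseline, r_SY = r_SB·r_BY and the share is 0.
- *Upper corner.* With r_SB = 0.6, r_SY = r_BY = 0.5 and a median cut (φ² = 0.1592, p(1 − p) = 0.25): 0.1592 × 0.04 / [(0.25 − 0.36 × 0.1592) × 0.75] = 0.00637 / 0.1445 = 4.4%. The standard error ratio is √(1 − 0.044) = 0.978, a fall of 2.2%.

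Simulated values (1,000,000 draws; Screening mean 10.5 and SD 3 assumed, so the cut is at about −0.17):

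| r_SB | r_BY | Screening acts only through baseline | Screening predicts as well as baseline |
|---|---|---|---|
| 0.6 | 0.3 | 0% | 1.28% |
| 0.6 | 0.5 | 0% | 4.34% |
| 0.7 | 0.5 | 0% | 2.71% |
| 0.8 | 0.5 | 0% | 1.38% |
| 0.9 | 0.5 | 0% | 0.43% |
| 0.95 | 0.5 | 0% | 0.13% |

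**Power.** 325/5 = 65 per arm; with the 6% missing that SAP 7.2.3 expects, about 61. The difference is 1.5 points (the Delta in the 7.2.6.9.5 code) and the residual SD is assumed to be 4. SE = 4√(2/61) = 0.724, so power ≈ Φ(1.5/0.724 − 1.96) = 54.4% for one unadjusted comparison. With SE × 0.978 it is 56.3%. The gain is therefore 0 to about 2 points.

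**Validity.** Single-visit ANCOVA, 325 subjects, five arms, stratified permuted blocks of 5 (assumed), total SD 4, 8,000 replicates for each of four correlation settings:

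- Type I error was 4.55% to 5.15% without the stratum and 4.51% to 5.28% with it (Monte Carlo SE √(0.05 × 0.95/8000) = 0.24 points).
- Mean estimates were within 0.01 of the truth in both models.
- In the corner 0.6/0.5/0.5 under the null, the mean reported SE fell from 0.6080 to 0.5947 (2.2%). The actual spread of the estimates moved only from 0.5991 to 0.5967 (0.4%). Stratified allocation had already delivered most of the precision; the fuller model mainly reports it.
- Power in that corner rose from 69.1% to 70.7%. It is higher than 54.4% because here 4 is the total SD and no data are missing.

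**The case against.** The case for leaving the model alone is substantial.

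- **It is a deliberate choice.** SAP 7.2.5 names the factor as a Screening score and sets it against the continuous baseline, so it does not confuse the two. A later, continuous reading with its own month interaction carries much of what an earlier two-level version could offer. This stands as a defensible preference. It does not make the stated reason complete.
- **The gain may be nil.** Nothing in the documents shows that the Screening category predicts Month 6 beyond baseline. The 4.4% needs two pre-treatment readings that correlate at only 0.6, with the older one predicting as well as the newer. This stands: the range starts at zero.
- **Consistency with other models is no argument.** A reader might infer that the primary model is the odd one out. The SRI-4 and BILAG GLMMs, the PGA MMRM and the TP1 Cox models do include both strata, but none contains a continuous mSLEDAI-2K term, so there the stratum is the only disease-activity adjustment. The Group 2 models in 7.5 list neither stratum, and the Group 1 MMRM in 7.5.2.2 reuses 7.2.5.
- **The stratum is not ignored.** It defines a subgroup and is tabulated IXRS against eCRF (6.8.2.2).
- **The edit is more than one line.** The imputation code in 7.2.6.1 to 7.2.6.3 has its own variable lists. This stands and is counted in the fix.

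**Conclusion.** The point holds as a low-cost improvement of small and uncertain size. Baseline does not fully determine the stratum, so the reason in 7.2.5 does not strictly follow, and no whole-sample analysis in Table 5 tests the omission. On assumed correlations, adding the stratum lowers the Month 6 residual variance by 0% to about 4.4%, the reported standard error by 0% to about 2.2%, and raises pairwise power by 0 to about 2 points at an assumed residual SD of 4. These are single-visit normal approximations to the MMRM.

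A reader might go further and infer that the primary analysis is invalid because it does not mirror the randomization, or that known prognostic information is thrown away. The documents support neither. The treatment comparison is unbiased without the stratum, and any departure in type I error is in the conservative direction. The information lost beyond baseline is unknown and may be zero.

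**What to change.** In SAP 7.2.5, add the IXRS mSLEDAI-2K stratum (sledai_sc, the variable already used in the 7.3.1.5 code) to the CLASS and MODEL statements as a fixed effect. Keep continuous baseline and its month interaction. Delete the sentence that excludes the stratum.

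Carry the term into the 7.2.6 analyses that reuse this model, including the code in 7.2.6.1.2. Add it to the matching imputation variable lists in 7.2.6.1 to 7.2.6.3, extending the positional minimum and maximum lists by one entry. In 7.2.7.2, omit it for the subgroup analysis by mSLEDAI-2K stratum, as is already done for OCS.

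The cost is one degree of freedom at about 325 subjects and minor code edits; no new data are needed. The change belongs before unblinding for the Month 6 analysis. If that has already happened, the model with the stratum should be reported as a labelled sensitivity analysis and the rationale in 7.2.5 corrected.
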